### 6.4.1 Pre-vaccination Questionnaire

All study participants, except those who were already vaccinated outside of the study, will complete a second brief questionnaire to determine whether they are currently experiencing fever, decreased energy, muscle aches, headache, or nausea, and will be asked to rate the subjective severity of any symptom(s) as mild, moderate, or severe (Appendix E. Prevaccination Questionnaire/Vaccine Administration Form). Appendix E will also readdress the study exclusion criteria. Participants reporting subjective fever (of any severity) and those reporting no fever but one or more symptom of moderate or severe subjective severity will not receive study vaccine until their illness has resolved. In this case, a follow up appointment will be made after resolution of the illness, at which time the participant will receive the vaccine. Study number assignment and pre-vaccination blood draw will take place on the day of vaccine administration.

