#### 1. PROJECT SUMMARY

Healthcare personnel (HCP) are believed to be at increased risk of influenza virus infection due to a higher rate of exposure compared with the general population. Close contact with patients may further result in transmission to patients. Vaccination is the most effective method of preventing influenza, but there is limited information on the effectiveness of influenza vaccines among HCP. Some studies have demonstrated reduced influenza vaccine immunogenicity and effectiveness among persons with a history of frequent influenza vaccination, emphasizing the need to examine influenza vaccine effects among HCP who may be frequently vaccinated or demonstrate a high baseline immune response to influenza viruses.

The primary objective of the study is to compare humoral immune responses to a single dose of recombinant hemagglutinin quadrivalent influenza vaccines (RIV4) or to standard egg-

based unadjuvanted quadrivalent influenza vaccines (IIV4) among  $HCP \ge 18$  years old who were vaccinated in the 2018-19 season with IIV4. The trial will be conducted at two hospital sites in Israel during the upcoming influenza season (2019-20) among HCP who were enrolled in the Study of Healthcare Personnel with Influenza and other Respiratory Viruses in Israel (SHIRI).

The study design is a randomized, single-blind, trial. During the study, eligible HCP at each site who consent to participate will be randomized 1:1 to receive a single dose of RIV4 (Flublok™ Quadrivalent by Sanofi, Inc., 45µg of HA per strain) versus a single dose of IIV4 (VaxigripTetra™ by Sanofi, Inc., 15µg of HA per strain). Participants will be blinded to the vaccine that they receive; study staff will not be blinded. Eligible HCP who report already having been vaccinated with Vaxigrip at the time they are approached to join the study will be eligible to participate. All randomized participants will have blood collected just prior to vaccination; all participants, including those who were vaccinated with Vaxigrip outside of the study, will have blood collected , approximately 28 days after to evaluate humoral immune responses to vaccination. Relative efficacy of single doses of study vaccines will be assessed by comparing immunologic responses to vaccination among participants receiving RIV4 and those receiving IIV4. In addition, the effect of prior vaccination in potentially modifying antibody immune responses to vaccine will be evaluated.

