## 6. METHODS

## 6.1 Overview of Study Design

This is a randomized, single-blind study design. Starting in July 2019, approximately 550 to 700 HCP from two hospitals (275-350 per hospital site) in Israel will be enrolled. Following completion of a written consent form, participants will complete an enrollment survey and grant permission for review of information collected during the SHIRI study, including vaccination status and immune response during the SHIRI study years. Participants will complete an enrollment survey and grant permission to include and integrate information collected during the SHIRI study into the current study's data, including health history, influenza vaccination history, and immune response to vaccination during the SHIRI study years. HCP will be randomly assigned 1:1 to receive a single dose of IIV4 licensed in Israel (expected to be Vaxigrip® Quadrivalent, 15µg of HA per strain) or RIV4 (Flublok® Quadrivalent by Sanofi Pasteur, 45µg of HA per strain) during August-October of 2019. Participants will be blinded to the vaccine that they vaccine, but study staff will be aware of the vaccine. Adverse events following vaccination will be monitored and documented. Blood specimens will be collected prior to vaccination and approximately 28 days after to evaluate immune responses to vaccination.

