## Exclusion criteria

- 1. Already received an influenza vaccine during the current influenza season
- 2. Not willing or able to get the flu vaccines being used in this study;
- 3. Previous hypersensitivity reaction to the study vaccines, or any vaccine, as reported by the subject
- 4. Received any non-influenza vaccine (e.g., Hepatitis B or other vaccine recommended for HCP) in the 4 weeks prior to the first study visit or plans to receive a vaccine in the 4 weeks following the first study visit
- 5. Currently participating in a study that involves an experimental agent (vaccine, drug, biologic, device, blood product, or medication), or has received an experimental agent within 1 month prior to enrollment in this study, or expects to receive an experimental agent during participation in this study.
- 6. Any condition or employment status that the potential participant or local study site principle investigator (PI) believes may interfere with successful completion of the study prior to December 2019, including being currently pregnant.

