#### 6.3.4 Randomization

Using the list of HCP consented to participate in the study, HCP will be randomized 1:1 to receive one 0.5 mL intramuscular dose of Flublok® Quadrivalent or Vaxigrip Quadrivalent. Randomization lists will be generated by the epidemiologist and data analyst using block randomization to ensure equal sample size in each group.

Randomization will be conducted after enrollment is completed. Randomization will occur separately for participants in Group One and Group Two.

Randomization will not occur for enrolled participants who were vaccinated with Vaxigrip outside of the study.

# 6.4 Study visit 1

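### Exclusion criteria are re-addressed at visit 1, after randomisation, with no step concealing allocation until then, so exclusions could depend on arm and would fall outside the intention-to-treat analysis as planned

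*Combined protocol and SAP*

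**What the plan says.** The sequence is spread over several sections of the combined protocol and SAP.

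- **Screening.** A study physician checks eligibility and takes consent (Section 6.3.3, Appendix B).
- **Randomisation.** "Using the list of HCP consented to participate in the study, HCP will be randomized 1:1" and "Randomization will be conducted after enrollment is completed" (Section 6.3.4). The lists are blocked, made separately for Groups One and Two, and generated by the epidemiologist and data analyst.
- **Calendar.** Enrolment starts in July 2019 and vaccination runs from August to October (Section 6.1), so weeks may separate the two.
- **Blinding.** "Participants will be blinded to the vaccine that they receive; study staff will not be blinded" (Section 1). Section 6.1 agrees: "but study staff will be aware of the vaccine".
- **Visit 1.** Participants complete a questionnaire on current symptoms, and "Appendix E will also readdress the study exclusion criteria" (Section 6.4.1). In the same section, "Study number assignment and pre-vaccination blood draw will take place on the day of vaccine administration".
- **The discretionary criterion.** Exclusion item 6 covers "Any condition or employment status that the potential participant or local study site principle investigator (PI) believes may interfere" with completing the study before December 2019.
- **Analysis.** Section 9.2 says that primary analyses are intention-to-treat. It does not define that set and gives no missing-data method. Sections 5.1 and 9.2 count SCR only among participants with paired samples.

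The plan does not say what happens to a randomised person who fails the re-check.

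**The concern.** Randomisation protects the comparison only if who stays in the trial does not depend on the assigned arm. Here eligibility is revisited after assignment, in a trial whose staff are declared unblinded, using a list that includes one criterion of opinion.

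The re-check is more than a formality. Item 4 (other vaccines within four weeks either side) is timed to the first study visit, so it can be settled only then. Influenza vaccination this season, pregnancy and the investigator's judgement under item 6 can all change after screening. Some exclusions after randomisation are therefore built into the design.

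The intention-to-treat label does not repair this. A person excluded at visit 1 has no required sample then and is not required to give one at visit 2. End-of-season serum from the earlier cohort study serves as baseline only for people vaccinated outside the study (Section 6.4.2), and it could not replace a missing post-vaccination titre. If exclusions differed between arms in number or kind, the SCR and fold-rise comparisons would absorb the difference, and the planned analysis has no means of correcting it.

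**Working it through.** **1. Order of events.** Table 3 puts screening and enrolment in a column before visit 1. Section 6.3.4 randomises from the consented list after enrolment, and the re-check belongs to visit 1. Whether enrolment there means each person's or the whole trial's, the text places randomisation before the re-check. That the re-check also precedes the blood draw is inferred from the order of Sections 6.4.1 to 6.4.3; the text fixes only that the draw is on the day of vaccination.

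**2. The plan's own figure.** Inputs from Section 9.1: two-sided 0.05, power 80%, SCR 40% with IIV4, 30% relative increase, so 0.40 × 1.30 = 52% with RIV4, a difference of 12 points. With pooled variance and no continuity correction:

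n per arm = [1.960·√(2 × 0.46 × 0.54) + 0.842·√(0.40 × 0.60 + 0.52 × 0.48)]² / 0.12² = 269.6, rounded up to 270, total 540.

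This is the Table 2 entry. The other eleven rows reproduce in the same way.

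**3. Scale of a possible bias.** The documents give no exclusion rate at the re-check and no SCR for those excluded, so both are assumed. Take no true effect, with SCR p = 0.40 in both arms. A share f of one arm only is excluded, and those people would have had SCR s. The remaining SCR in that arm is p′ = (p − f·s)/(1 − f), so the spurious difference is

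d = f·(p − s)/(1 − f).

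Type I error uses the 440 people of Group One, 220 per arm before exclusions and ignoring dropout:

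se = √[p(1 − p)/220 + p′(1 − p′)/(220(1 − f))], error = 1 − Φ(1.96 − d/se) + Φ(−1.96 − d/se).

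| f, one arm only | d in points, s = 0.30 to 0.10 | Two-sided type I error |
|---|---|---|
| 2% | 0.2 to 0.6 | 0.050 to 0.052 |
| 5% | 0.5 to 1.6 | 0.051 to 0.063 |
| 10% | 1.1 to 3.3 | 0.056 to 0.106 |

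Worked case, f = 0.10 and s = 0.10: d = 0.10 × 0.30/0.90 = 0.033; se = √(0.24/220 + 0.2456/198) = 0.048; d/se = 0.69; error 0.106.

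The sign is not determined. If the excluded people sat in the other arm, or had s above 0.40, d would reverse.

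**4. Numbers lost.** Power at 40% against 52% is 80.8% with 550. After the planned 5% dropout and a further 2%, 5% or 10% lost at the re-check from both arms (assumed additional), 512, 496 or 470 remain, with power 77.9%, 76.6% or 74.4%. This loss arises whether the re-check comes before or after allocation, so it does not count for or against the present order.

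**The case against.** The strongest reply is that the text never puts the allocation in the hands of the person handling Appendix E. Unblinded staff is a general statement. Participants, who are blinded, complete the questionnaire. The lists come from the epidemiologist and data analyst, and the study number is assigned only on vaccination day, so the allocation may become operational only then. A reader might infer that staff know the arm when they re-apply the criteria; the documents do not say so. They describe no concealment either, which is all that the point needs.

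Second, most criteria leave little room for staff judgement. Items 1, 4 and 5 are factual, item 2 turns largely on the blinded participant, and item 3 is self-reported. Item 6 asks about finishing the study, not about suitability for one vaccine. This stands and narrows the route to item 6, together with the investigator's power in the withdrawal criteria to remove people for unspecified reasons.

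Third, a reader might infer that staff would be more cautious with RIV4, which is unlicensed in Israel and has three times the antigen per strain, and that the bias would therefore favour RIV4. The documents do not support that direction. Section 3.1 reports equivalent reactogenicity, Section 8 reports events comparable to or often less frequent than with inactivated vaccine, and nothing shows that those excluded would respond poorly.

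Fourth, people vaccinated elsewhere while waiting might seem to be a further arm-dependent loss. They are blinded to arm, and the withdrawal criteria already cover them, so no such dependence is shown.

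Fifth, a physician has already screened everyone, so the re-check should catch mainly changes since then. An exclusion of 10% in one arm is twice the plan's 5% allowance for dropout before visit 2. The lower rows of the table are the more plausible ones.

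Finally, releasing allocations one at a time from fixed blocks could let unblinded staff predict later ones. That is a fair warning about how the remedy is built, and the fix takes account of it.

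**Conclusion.** The point holds as a gap in procedure. Randomisation precedes a re-check containing a discretionary criterion, staff are stated to be unblinded, nothing conceals the allocation until the re-check is done, and people excluded there drop out of an analysis described as intention-to-treat. Arm-dependent exclusion is possible on the text. It is not shown to be likely, to favour either vaccine, or to have any particular size.

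On assumed one-arm exclusion of 2% to 10%, with SCR of 10% to 30% among those excluded, the spurious difference is about 0.2 to 3.3 points against the planned 12. At 2% it hardly moves the type I error (at most 0.052); only the extreme case roughly doubles it (0.106). The change is worth making because it is cheap and removes the question. The point does not invalidate the design.

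**What to change.** Amend Sections 6.3.4, 6.4.1 and 9.2 as follows.

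1. Keep the per-person allocation list, stratified by group as now, with the data analyst, for example in REDCap, which Section 6.7 already uses for the surveys. Do not disclose block sizes to site staff. With the list drawn up per person and held centrally, staff have no sequence from which to predict the next assignment.
2. Reveal a person's allocation only after the Appendix E re-check is signed and the baseline blood is drawn.
3. Define the intention-to-treat set as everyone whose allocation was revealed.
4. Report exclusions before reveal and withdrawals after reveal, by arm and with reasons. Because each person already has a listed allocation, exclusions before reveal can be tabulated by arm at the analysis, which checks that concealment worked.

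The exclusion criteria and Table 2 stay as they are. The cost is one concealment step and having both vaccines on hand at each session; Section 8 gives them the same storage temperature. The change does not deal with people who are revealed, vaccinated and then miss visit 2. They belong to the intention-to-treat set, and Section 9.2 still needs to say how their missing titres are handled.

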#### 6.4.2 Blood Draw

All study participants will have 20 ml of venous blood drawn for serologic testing at the first study visit via venipuncture in multiple serum separator tubes with clot activator and gel, according to CDC guidelines. The use of a butterfly needle connected to a vacutainer tube is recommended as the best collection method to minimize hemolysis and to reduce the risk of needle stick injury. As an alternative, the use of a safety needle that connects directly to the vacutainer tube is acceptable. Study staff will document the blood collection in **Appendix F1: Blood Specimen Collection/Tracking Form.** 

Study participants who were vaccinated with Vaxigrip outside of the study will not receive a blood draw during the initial study visit. For these participants, the end-of-season blood draw from SHIRI, which was taken at the end of the 2018-2019 influenza season, will be used as their "pre-vaccination" or "baseline" blood draw.

#### 6.4.3 Vaccine administration

Participants will receive a single (0.5ml) dose of study vaccine administered in the deltoid muscle of the arm opposite the blood draw. Vaccine administration will be performed by a qualified nurse trained in the delivery of the study vaccines and documented on **Appendix E. Pre-vaccination Questionnaire/Vaccine Administration Form**. Participants will not be made aware of the vaccine they received until after the second blood draw (Study visit 2).

# 6.5 Study Visit 2

The optimal timing for Study Visit 2 is 21 to 35 days after vaccination, though 21 to 62 days will be considered acceptable. All study participants will have 20 ml of venous blood drawn for serology testing. Study staff will document the blood collection in **Appendix F1: Blood Specimen Collection/Tracking Form.** 

# 6.6 Post-vaccination safety monitoring

After receiving the vaccine, all randomized participants will be contacted by SMS or by telephone 2-3 days post-vaccination and asked about adverse events (Appendix I). Non-solicited reports of adverse events will be documented from the time of vaccination through the second blood draw. Adverse events reported during this time period that are deemed to be serious by a medical doctor will be investigated. Serious adverse event reporting forms will be completed according to Israel Ministry of Health guidelines. In addition, study staff will provide participants with a phone number to call in case they have any questions or concerns about possible adverse events after vaccination.

#### 6.7 Data Collection

Linked SHIRI Data: The participants of the current study are identified from among HCP that previously participated in the SHIRI study during the 2016-2019 influenza seasons. Subject to participant consent, study investigators will link all data from the previous study with data collected during the current study. This reduces participation burden, since previously supplied information does not need to be repeated, and provides information that is essential to study objectives, including immune profiles in previous seasons and HI response to prior vaccinations.

Enrollment Survey: Updated information on participants' health and occupational responsibilities will be collected by self-report though brief surveys at enrollment. Surveys are designed to be self-administered electronically via the internet using the REDCap program. In rare cases when a participant cannot complete a survey on his or her own, study staff will administer the electronic survey to the participant by telephone or in-person. Data collection elements are outlined in the Enrollment Questionnaire (**Appendix D. Enrollment Questionnaire**).

Electronic Medical Record (EMR) Extraction: For all enrolled HCP, additional data will be extracted from the Clalit Health Services (CHS) EMR, which contains extensive demographic and clinical data. Information on socio-demographic characteristics, chronic medical conditions,

medical care utilization, and influenza vaccination history (including date of receipt, vaccine product name, vaccine lot number, and route of administration) for the preceding 10 years will be extracted from CHS medical records and employee records at enrollment.

#### 7. LABORATORY PROCEDURES

# 7.1 Blood Collection/Processing/Storage

After collection, blood specimens will be transported to the local laboratory for processing using standard procedures. Each tube will be labeled or barcode linked with the participant ID number, study visit number, and date of collection. Collected blood will be stored at 4°C immediately either by placing the sample on ice, in a 4°C refrigerator, or in a cooler with cold packs. Blood may be stored at 4°C for up to 18 hours. Sometime between 1 hour and 18 hours after collection, the blood collection tube will be centrifuged to separate the clotted blood from the serum and the serum removed to a clean tube labeled or barcode linked with the study participant ID number, study visit number, and date of collection. The clotted blood will be discarded. The serum will then be divided into approximately 8-10 aliquots of 1 mL/aliquot into labeled tubes. After aliquoting, the serum samples will be immediately stored at -20°C or colder.

Participant specimens will be stored indefinitely at a CDC-designated facility for future testing to evaluate aspects of respiratory infection and/or immune responses to influenza vaccine or influenza virus infection, as needed. Participants will also be asked if they would like to be contacted about future research studies related to this study.

### 7.2 Specimen Testing

Assessment of humoral or serologic immune response to antigens that match influenza virus strains that are components of the vaccines and circulating during the study period typically require multiple laboratory assays. We expect that primary methodologies for this effort will be the HI and MN assay. In recent years, MN assays have been required to assess response to cell-grown A/H3N2 viruses, which are a better match to circulating strains and vaccine strains in vaccines that do not involve egg-based production, such as Flublok. Nonetheless, the combination of assays and antigens most relevant to the study objectives will depend on vaccine components, circulating strains, and performance of assays during the study period.

Additional advance serologic assays on a subgroup of specimens may be required. For example, to examine the extent of narrow vs. broad antibody responses and the potential overfocusing of response on specific antibody sites, it may be necessary to quantify inhibition by serum of antigenic site-specific monoclonal antibodies (mAbs) to HA. Response to the two vaccine types may also differ in the extent "back boosting" of antibodies to historical vaccine and circulating viruses as measured by conducting an antibody landscape.

Sera will be tested by HI and MN to measure antibody titers against cell-grown and egg-grown vaccine reference viruses at approximately 28 days post-vaccination compared to baseline samples drawn at day 0 prior to vaccination during each study season. Sera may also be tested by HI and MN against cell-grown wild-type influenza strains, as appropriate. MDCK-SIAT cells or another appropriate cell line will be used to cultivate cell-grown virus strains. A subset of sera from each study arm may also be tested by other immunologic assays as appropriate to measure activity against antigens represented in the study vaccines at day 0 and at approximately 28 days at each site.

#### 8. VACCINE PRODUCT

Two vaccine products will be used in this trial: (1) the standard-dose quadrivalent inactivated influenza vaccine (expected to be Vaxigrip® Quadrivalent), and (2) Flublok® Quadrivalent. CDC or study sites will purchase vaccine. Both vaccines are inactivated influenza vaccines that are approved for use in adults aged ≥18 years in the United States. Vaxigrip Quadrivalent is licensed in Israel. Flublok is not licensed in Israel. Both vaccine products will contain vaccine strains representative of the four strains in the 2019-2020 northern hemisphere formulation.

Vaxigrip® Quadrivalent is a split-virus/subvirion vaccine manufactured by Sanofi Pasteur. It is formulated from influenza virus grown on embryonated chicken eggs. Vaccine virus is harvested, inactivated with formaldehyde, purified by zonal centrifugation using a sucrose gradient, split by Triton® X-100, and then further purified to a split-virus/subvirion form. The resulting vaccine suspension is clear and is available for use in adults as a prefilled single-dose 0.5mL syringe or a 5mL multi-dose vial; the vaccine is administered intramuscularly. Each dose is formulated to contain 15µg of HA per strain. Each 0.5mL dose of vaccine also contains sodium phosphate-buffered isotonic sodium chloride solution, up to 100µg of formaldehyde, and up to 250µg of octylphenol ethoxylate. Multi-dose vials also contain the preservatives,

thimerosal and mercury. The most common reactions occurring after vaccine administration in adults are pain at the injection site, myalgia, headache, and malaise. The vast majority of these reactions are mild to moderate, and severe reactions are very rare.

Flublok® Quadrivalent is a recombinant vaccine manufactured by Sanofi Pasteur. The vaccine is formulated from purified HA protein from cell-culture isolates of the vaccine reference virus grown using baculovirus vector technology in an insect cell line (*expres*SF+®) from cells of the fall armyworm. Influenza HA is removed from cells using Triton® X-100 and then purified by chromatography. The resulting vaccine suspension is clear and is available for use in adults as a prefilled single-dose 0.5mL syringe for intramuscular administration. Each dose is formulated to contain 45μg of HA per strain. Each 0.5mL dose of vaccine also contains 4.4mg of sodium chloride, 0.195μg of monobasic sodium phosphate, 1.3mg of dibasic sodium phosphate, and 27.5μg of polysorbate 20. The vaccine may also contain up to 19mcg of baculovirus and *Spodoptera frugiperda* cell proteins, up to 10ng of baculovirus DNA and cellular DNA, and up to 100μg of Triton X-100. The most common systemic symptoms after vaccine administration are injection site tenderness or pain, headache, fatigue, muscle pain, and joint pain. Severe reactions are very rare. The frequency of solicited symptoms and adverse events were comparable or often less frequent than among IIV recipients.

Vaccine products will not be modified for this study. The vaccines must be stored at 2° C to 8° C [35.6° F to 46.4° F] until needed. Vaccine products should not be frozen and should be protected from natural light. Documentation of proper vaccine storage will be monitored daily and maintained during the duration of the trial. In the event of accidental deep-freezing or disruption of the cold chain, study vaccine will not be administered.

